7.2 THE NUMBER OF PARTICIPANTS

Minimally clinical important difference of 20mm will be used as the clinically admissible margin of non-inferiority. From previous studies, it is assumed to use a standard deviation of 25mm and with a 95% power calculations have determined a required sample size of 41 per study arm, when including a 20% fall out rate a total sample size of 100 patients will be required²².

7.3 THE LEVEL OF STATISTICAL SIGNIFICANCE

. All statistical testing was done at the two-sided 5% significance level, and 95% CIs with Stata 14.2.

7.4 RANDOMISATION

Patients will be randomised using the simple randomisation service provided by Sealed Envelope Ltd (<https://www.sealedenvelope.com>). This is an online service that provides random permuted block randomisation, ensuring participants are balanced between the control and treatment group.

7.5 CRITERIA FOR THE TERMINATION OF THE TRIAL.

Once 100 patients have been recruited and randomised to the trial.

7.6 PROCEDURE FOR ACCOUNTING FOR MISSING, UNUSED, AND SPURIOUS DATA.

A 20% fall out rate has been considered. Participants who have not returned their patient assessment records will not be included in the analysis. Results from partially completed forms will be included for analysis.

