3. STUDY DESIGN

This is a single site, patient and assessor blinded, non-inferiority randomised control trial where patients will be randomised to receive an injection of corticosteroid alone or an injection of corticosteroid co-administered with local anaesthetic to treat; trigger finger, de Quervains tenosynovitis or carpal tunnel syndrome.

The reviewing physician will identify eligible patients during 20-minute outpatient hand and wrist clinic appointments. Providing that the patient meets the inclusion and exclusion criteria the supernumerary registrar in clinic will explain the study to the patient and provide them with an information leaflet (Appendix 1). Patients considering enrolment will return to the waiting room to read the study information. This allows sufficient time for the patients to go through the information at their own pace and for the clinic to continue to avoid it running behind. The patients can have the duration of the morning clinic (if required) to consider enrolment in the study. After the patients have read the study information they will return to clinic as soon as they are ready and be seen by the registrar a separate clinic room. There will be no pressure to participate and if patients do not want to be included they will still receive treatment within the clinic, as they would do normally.

Normal practice for patients attending outpatient hand and wrist clinic with a clinical diagnosis of trigger finger, de Quervains tenosynovitis or carpal tunnel syndrome:

Once the patient feels well informed and comfortable to participate, consent will be received (Appendix 2) and a patient participation record completed (Appendix 3). A photocopy of the consent form will be given to the patient and another copy kept in the patients' hospital notes. The original consent form will be kept in the site file along with the patients' participation record. The patient participation record contains a patient participation number, which is the only link between the patient and the treatment

delivered. The supernumerary registrar uses a computerised randomisation system to randomise the patient into one of the two treatment arms, whilst the patient completes the pre-injection validated pain VAS score on the patient assessment record (Appendix 4).

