Patients will be randomised using the simple randomisation service provided by Sealed Envelope Ltd. This is an online service that provides random permuted block randomisation, ensuring participants are balanced between the control and treatment group. The physician will use a unique URL and password to randomise patients in A (treatment) or B (control) group.

Patients will receive injections containing one of the two following solutions, delivered under landmarks guidance to treat either; trigger finger, de Quervains tenosynovitis or carpal tunnel. Both combinations are used as part of routine practice for soft tissue corticosteroid injections in the hand and wrist at University Hospital NHS Trust by the local Hand and Wrist surgeons:

- A. 1ml of triamcinolone (40mg/1ml)
- or
- B. 1ml of triamcinolone (40mg/1ml) + 1ml 1% Lidocaine

The registrar will draw up, prepare the treatment in a separate room so that the patient will remain blinded. Neither treatment can be distinguished from one another by their appearance alone.

During the clinic appointment the patient will complete a pain VAS score prior to the injection, for pain experience at the time of the injection and at 5 minutes post injection on the patient assessment record. The pain VAS score of the pain experience during the corticosteroid steroid will be recorded immediately after the procedure. The patient then takes the patient assessment record home to complete further pain VAS scores at; 1-hour, 2-hour, 3-hour and 24-hours following the injection. The timings at which these scores must be recorded will be clearly documented on the patient assessment record by the physician before leaving clinic to help remind the patient. There are three further questions, on the same form; that the patient will be required to answer at 3-hours post injection (Appendix 4).

During the first 3-hours after your steroid injection:

1. Did you take any additional painkillers because of pain at the injection site?

YES Medication: _____

Time taken: _____

NO (go to next question)

2. Did you have any reduction in hand function, below normal, as a result of the injection?

YES please describe your reduction in function:

NO

3. Did you experience any new numbness in your hand, as a result of the injection?

YES

NO

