7. STATISTICS AND DATA ANALYSIS

7.1 DESCRIPTION OF STATISTICAL METHODS

The primary objective;

Investigate whether there is a difference in pain VAS scores at 1-hour after a corticosteroid injection for trigger finger, de Quervains tenosynovitis or carpal tunnel syndrome administered with or without local anaesthetic.

Primary outcome measure of primary objective:

1a) A analysis of the mean change in pain VAS score between 1-hour post injection and baseline pre-injection will be performed. The primary intention will be the use of parametric tests

(Unpaired Students T-test) dependent upon the assessment of score distribution (skewness and kurtosis). Non-parametric testing will be employed if the mean distribution fails tests of normality.

Secondary outcome measures of primary objective:

1b) The effect size at 1-hour post injection will be calculated to measure the significance of the difference between the study and control group.

Mean score at 1-hour in corticosteroid alone group	-	Mean score at 1-hour in corticosteroid and LA group
Standard deviation		

The objectives;

i) Additional sensitivity analysis will be conducted to investigate whether there is a difference in pain VAS scores during the 24-hours after a corticosteroid injection for trigger finger, de Quervains tenosynovitis or carpal tunnel syndrome administered with or without local anaesthetic.

Outcome measure: The cumulative pain in the 24-hour period in both groups will be calculated by using the area under the curve. Multilevel linear regression analysis will be conducted to compare 24 hour pain VAS with injection intervention nested in patient condition.

ii) Additional sensitivity analysis will be conducted to investigate whether there is a difference in the pain VAS scores at the time of the corticosteroid injection for trigger finger, de Quervains tenosynovitis or carpal tunnel syndrome administered with or without local anaesthetic.

Outcome measure: the pain VAS scores in each group at the time of the injection. Multilevel linear regression analysis will be conducted to compare pain VAS with injection intervention nested in patient condition.

iii) Investigate the difference in the additional analgesia required and in the functional use of the hand during the first 3 hours following a corticosteroid injection for trigger finger, de Quervains tenosynovitis or carpal tunnel syndrome administered with or without local anaesthetic.

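### Condition enters the secondary models but neither stratifies the allocation nor appears in the primary comparison, so the mix of three conditions across arms is left to chance

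*Combined protocol and SAP*

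**What the plan says.** **Allocation.** Sections 3 and 7.4 are the only descriptions, and they agree: "This is an online service that provides random permuted block randomisation, ensuring participants are balanced between the control and treatment group". Both also use the word simple in naming the service, but what they describe is permuted blocks, and I take that as the design. Neither section names a stratification factor, a block length, or whether the length varies.

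**Analysis.** In section 7.1 the primary comparison is an unpaired t-test on the change in VAS from baseline to 1 hour, with a non-parametric fallback and no covariates. Condition appears only in the multilevel models for 24-hour pain and for pain at injection, each fitted "with injection intervention nested in patient condition".

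**Who does what.** Section 3 says: "The supernumerary registrar uses a computerised randomisation system to randomise the patient into one of the two treatment arms". A few lines later it gives that task to the physician, by URL and password. On preparation it says: "The registrar will draw up, prepare the treatment in a separate room so that the patient will remain blinded". The reviewing physician identifies eligible patients (sections 3 and 4.1), a consultant makes the diagnosis (section 4.3), and consent is described before randomisation.

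**Sample size.** Section 7.2 sets the margin: "Minimally clinical important difference of 20mm will be used as the clinically admissible margin of non-inferiority". It takes the SD to be 25 mm, and for 95% power arrives at 41 patients in each arm.

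**The concern.** The plan treats condition as worth modelling for two secondary outcomes, but uses it in neither the design nor the analysis of the outcome that decides the trial. There is some reason to think it could matter. The section 4.3 criteria require localised pain for trigger finger and de Quervains tenosynovitis, but not for carpal tunnel syndrome. A patient who starts with little pain has less room to fall, so the change score may depend on condition.

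Blocking fixes the arm totals only. If the arms differ in their mix of conditions, an unadjusted difference carries part of the between-condition difference with it. At stake are some precision and an avoidable question when the baseline table is read.

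**Working it through.** **1. The plan's own figure.** Inputs from sections 7.2 and 7.3: margin 20 mm, SD 25 mm, 95% power, two-sided 5% (one-sided 2.5% for non-inferiority), no true difference.

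n per arm = 2 × (1.960 + 1.645)² × 25² / 20² = 2 × 13.0 × 1.5625 = 40.6, so 41. This reproduces the stated 41 (power 95.2%). The total of 82 becomes 103 as 82/0.8, or 99 as 82 × 1.2; the stated 100 is close to both. The formula contains no stratification term, so nothing below changes the sample size.

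Standard error at 41 per arm = 25 × √(2/41) = 5.5 mm.

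**2. How uneven the mix can be.** The documents give no case mix. Assume one condition has 20 of 100 patients, with 50 per arm. The number in one arm is hypergeometric: P(x) = C(20,x) × C(80,50−x) / C(100,50).

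| Split, either direction | Probability |
|---|---|
| 13:7 or worse | 21.1% |
| 14:6 or worse | 7.8% |

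Simulating actual permuted blocks of 4 and 6 gave 20.6–20.9% and 7.6–7.9%, so blocking without strata does nothing for condition balance. A wider simulation assumed mixes of one third each, 60/10/30 and 50/20/30, with blocks fixed at 4 or varying among 4, 6 and 8. The largest gap in any condition's share was at least 10 percentage points in 49–61% of trials and at least 20 points in 7–11%.

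**3. What that does to the estimate.** A 14:6 split is 28% against 12%, a gap of 16 points. Assume the condition differs from the others by 10 to 20 mm in mean change:

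- 0.16 × 10 = 1.6 mm
- 0.16 × 20 = 3.2 mm

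These are 0.3 and 0.6 of a standard error, and 8% and 16% of the margin. In the wider simulation, with 20 mm between the extreme conditions (assumed), the chance shift had an SD of 1.6–1.8 mm and a 95th percentile of 3.2–3.6 mm.

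**4. What adjustment buys.** If condition explains a share R² of the variance, N analysed patients with adjustment are worth N/(1 − R²) without it. With 80 analysed (100 less 20%) and R² = 5% (assumed): 80/0.95 − 80 = 4.2 patients.

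The assumptions in step 3 bracket this. Between-condition variance is 0.2 × 0.8 × d², which is 16 for d = 10 mm and 64 for d = 20 mm. Against 25² = 625, R² is 2.6% and 10.2%, and the gain is 80 × 0.026/0.974 = 2 patients to 80 × 0.102/0.898 = 9 patients.

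**5. Predictability, conditional only.** Suppose the block length were fixed, and known to someone who had seen every earlier allocation. With k = half the block length, the share of allocations certain in advance is 1/(k + 1): 50% for length 2, 33% for 4, 25% for 6. Neither condition is established by the documents.

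**The case against.** Much of the opposing case is sound.

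- Unstratified randomisation is unbiased in expectation. Any between-condition spread within the assumed 25 mm SD is already in the 5.5 mm standard error. This stands.
- The 1.6–3.2 mm rests on an assumed share and an assumed difference. Nothing in the documents shows that the 1-hour change differs by condition. Section 1.1 describes all three conditions as painful, and a change score subtracts baseline. This stands as to size. It does not explain why condition belongs in the secondary models and not in the primary one.
- The 7.8% counts both directions; a split that bad against corticosteroid alone occurs in 3.9% of lists. Even then, with a 3.2 mm shift, power is about 86% by the normal approximation: (20 − 3.2)/5.52 − 1.96 = 1.08. This stands.
- Stratification adds little once condition is in the model. Largely true, so the model term comes first in the fix.

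A reader might go further and infer that the registrar, who randomises and draws up each injection, can foresee the end of each block and so steer recruitment. The documents do not support that. They give neither a block length nor whether it varies. The registrar is a role that several people might fill, and another sentence gives the task to the physician. Eligibility and diagnosis lie elsewhere, consent precedes allocation, and the person who measures and analyses the VAS is blinded. What remains is that the plan does not rule out fixed, guessable blocks, and the registrar does lead the discussion before consent.

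**Conclusion.** The point holds at a modest size. Condition is in the secondary models but in neither the allocation nor the primary test, so its balance is left to chance. Under the stated assumptions (one condition with 20 of 100 patients, a 10–20 mm difference between conditions), a 14:6 split or worse occurs in about 7.8% of lists and moves the estimate by 1.6–3.2 mm. That is less than one standard error and at most 16% of the margin. It should not be called bias, and it does not threaten the non-inferiority conclusion or the stated sample size. The case for change is that it costs almost nothing, recovers roughly 2 to 9 patients' worth of precision (about 4 at R² = 5%), and aligns the primary analysis with the secondary ones. Predictable allocation is not a finding here; it is a detail to state.

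**What to change.** **Section 7.1, primary comparison.** Replace the plain t-test with a linear model for the 1-hour change that has treatment and condition (three levels) as fixed factors, and report the treatment difference with its 95% confidence interval. If the non-parametric fallback is needed, use a rank test stratified by condition. A main effect of condition is not a subgroup analysis, so that exclusion can stay. Cost: one model term.

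**Sections 3 and 7.4.** Stratify the permuted-block list by condition. Cost: a list setting, and up to three incomplete blocks at the end, so arm totals may differ by a few patients. With blocks of 4 (assumed), each unfinished block can differ by at most 2, so the worst case is 6.

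**Clarifications in the same sections.** State that block lengths vary at random and are not disclosed to recruiting staff, leaving the lengths themselves out of the protocol. Reconcile the registrar and the physician in section 3 as the person who randomises. Cost: wording only.

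The sample size of 41 per arm and 100 in total is unaffected.

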After the final pain VAS score at 24-hours the patient will receive a follow-up call by the registrar to ensure the assessment form has been completed, to answer any questions and remind the patient to

[figure not shown]
return the form using the prepaid envelope provided. After the form is posted the patients participation in the study will be complete.

The routine dictated clinic letter completed by the physician will outline the patients diagnosis, inclusion into the trial, and an overview of the trial and the consent process, but will not specify which treatment was delivered. A copy of this letter is kept in the patients' notes and a copy is sent to the GP.

The patient participation record and a copy of the consent form will be kept in the site file and stored in a locked filling cabinet in [name], Level 11, Derriford Hospital.

Returned patient assessment records will be collected by the departmental secretary, held within the site file and remain sealed until the end of recruitment. Once the recruitment phase is completed the patient assessment records will be open and the pain VAS scores will be measured, recorded on an excel spread sheet then statistically analysed by a blinded assessor ([name] - A member of the study management team, but directly not involved in patient recruitment). The same individual, who will not be involved in patient recruitment, will take all the measurements. Measurements will be taken using a standard 20cm ruler with 1mm increments and recorded to the nearest. Incomplete patient assessment records will be included on an intention to treat basis. A summary of the investigations, treatment and assessment can be found in Appendix 5. A planned time for the SToICAL study is outline in a Chart (Appendix 6)

Patient recruitment process during outpatient clinic:

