3.1 STUDY OUTCOME MEASURES

Patients pain will be measured using a 100mm pain VAS score which they will complete on a paper form; before the injection, at the time of injection, then 5-minutes, 1-hour, 2-hours, 3-hours and 24-hours after the injection. Patients will remain active in the study until the final VAS score is completed and the form is returned.

Assessment of additional analgesia required and any reduction in hand function will be determined by the patients answers to the following three question, which are completed 3-hours after the injection (Appendix 5).

During the first 3-hours after your steroid injection:

1. Did you take any additional painkillers because of pain at the injection site?

YES Medication: _____

Time taken: _____

NO (go to next question)

2. Did you have any reduction in hand function, below normal, as a result of the injection?

YES please describe your reduction in function:

NO

3. Did you experience any new numbness in your hand, as a result of the injection?

YES

NO

The study will end once 100 patients have been recruited, which includes 82 patients to achieve 95% power, plus 20% to account for potential dropouts. With an average of 3.6 corticosteroid injections given every week and an estimated 60% capture rate, full recruitment should be achievable within 12 months.

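### Partial forms are to be included, but the 1-hour change test drops any form lacking either of its two marks, and nothing says how a 24-hour AUC is formed without the 24-hour mark

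*Combined protocol and SAP*

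**What the plan says.** Pain is marked on one paper form "before the injection, at the time of injection, then 5-minutes, 1-hour, 2-hours, 3-hours and 24-hours after the injection" (section 3.1). The first three marks are made in clinic; the rest are made at home and the form is posted back.

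- **Incomplete forms.** Section 3: "Incomplete patient assessment records will be included on an intention to treat basis". Section 7.6: "Results from partially completed forms will be included for analysis". Section 7.7 puts everyone randomised who returned a form into an intention-to-treat analysis.
- **Unreturned forms.** Section 7.6: "Participants who have not returned their patient assessment records will not be included in the analysis".
- **Primary analysis (7.1).** "A analysis of the mean change in pain VAS score between 1-hour post injection and baseline pre-injection will be performed", by "Unpaired Students T-test) dependent upon the assessment of score distribution (skewness and kurtosis"; a non-parametric test is used if normality fails.
- **Objective i (7.1).** "The cumulative pain in the 24-hour period in both groups will be calculated by using the area under the curve". The next sentence reads "Multilevel linear regression analysis will be conducted to compare 24 hour pain VAS", with intervention nested in condition.

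The plan gives no imputation method, no minimum set of marks for an AUC, no scaling to observed time and no sensitivity analysis for missing data. The sensitivity analyses named in 7.1 are the secondary objectives themselves.

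**The concern.** The inclusion rule and the named analyses do not fit together. A participant who returns the 5-minute, 2-hour and 3-hour marks but misses the 1-hour mark counts as included under 3, 7.6 and 7.7, yet contributes nothing to the primary comparison. If missing a mark is related to pain or to arm, the non-inferiority estimate can be biased.

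For objective i, nothing is measured between 3 and 24 hours, so the AUC depends heavily on the last mark. Without a rule, the analyst must choose between leaving the AUC missing, imputing it, carrying a score forward or cutting the area short. These choices can give very different values.

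The regression wording adds a second uncertainty. If it means the single 24-hour score, it tests a different variable from the stated outcome, at a time 21 hours beyond lidocaine's longest effect given in section 1.1 (24 − 3 = 21).

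**Working it through.** **1. The plan's sample size.** Inputs from 7.2 and 7.3: margin 20 mm, SD 25 mm, power 95%, two-sided 5% (one-sided 2.5% for the non-inferiority bound). With a true difference of zero,

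n per arm = 2 × (1.960 + 1.645)² × 25² / 20² = 40.6, so 41.

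This matches the plan. Adding 20% gives 82 × 1.2 = 98.4, which the plan rounds to 100.

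**2. Primary power if 1-hour marks are missing.** A 20% loss from 100 leaves 80, or 40 per arm. Power = Φ(20 / (25 × √(2/n)) − 1.960). The documents give no missing rate per mark, so the extra losses are assumptions.

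| Usable forms per arm | Basis | Power |
|---|---|---|
| 40 | 20% loss as planned | 94.7% |
| 36 | further 10% lack the 1-hour mark (40 × 0.9) | 92.4% |
| 32 | further 20% lack it (40 × 0.8) | 89.3% |

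**3. Weight of the 24-hour mark.** With the trapezoid rule (assumed; the plan names none) on 0, 5 minutes, 1, 2, 3 and 24 hours, the last interval is 21 of 24 hours, or 87.5% of the time axis. The 24-hour mark takes half of it: 10.5 / 24 = 43.75%.

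**4. Two ways of handling a missing 24-hour mark.** The plan specifies neither, and all the pain courses below are assumed.

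| VAS (mm) at 0, 5 min, 1, 2, 3, 24 h | Area to 3 h (mm·h) | Full area (mm·h) | Cut at 3 h / full | 3-h score carried forward / full |
|---|---|---|---|---|
| 30 throughout | 90 | 720 | 0.125 | 1.00 |
| 50, 45, 40, 35, 30, 10 | 112.9 | 532.9 | 0.21 | 1.39 |
| 60, 50, 40, 30, 20, 0 | 105.8 | 315.8 | 0.34 | 1.67 |
| 50, 20, 10, 20, 40, 30 | 61.7 | 796.7 | 0.08 | 1.13 |
| 50, 30, 10, 15, 30, 50 | 56.7 | 896.7 | 0.06 | 0.77 |

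**5. Effect on an arm comparison, if areas were cut.** Suppose the 24-hour mark is missing in 10 percentage points more patients in one arm. At constant 30 mm the false difference is 0.10 × (720 − 90) = 63 mm·h, and 63 / 24 = 2.6 mm averaged over the day. The non-flat courses lose 210 to 840 mm·h per form, giving 0.9 to 3.5 mm. At 20 points the figures double: 5.3 mm for constant pain, and about 1.8 to 7.0 mm for the others. The arm with more missing marks would appear to have less pain.

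**The case against.** A reader might infer that the plan will produce 24-hour AUCs one eighth of their true size. The documents do not support that. No section says the area stops at the last mark; an analyst could leave it missing or impute it. One eighth is 3 h / 24 h and needs constant pain. Section 1.1 describes a flare starting after 90 minutes (in intra-articular injections) and lidocaine lasting 1 to 3 hours, so constant pain is not the expected course.

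Nor does every partial form fail. One lacking only the 24-hour mark is fully usable in the primary test. Objective ii uses a mark made in clinic, and objective iii is descriptive. A missing baseline is unlikely because it is also marked in clinic. Times are written on the form, patients are blinded, and the registrar telephones after 24 hours to check completion. These measures should reduce missing 24-hour marks and make a large imbalance between arms less likely.

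The regression wording directly follows the sentence on cumulative pain, so shorthand for the AUC is at least as natural a reading as a single score.

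All of this limits the size of the point. What remains is that the call is not an analysis rule, and it comes too late for the 1-hour mark, which could then be filled in only from memory. The primary test still has no value for a form without that mark, and the AUC still has no rule.

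**Conclusion.** The point holds as a mismatch between the inclusion rule and the analyses, together with a missing rule; it does not show that the planned results will be wrong. On the primary outcome, forms without the 1-hour or pre-injection mark leave the t-test. Power stays near 90% even at an assumed further 20% loss, so the larger risk is bias if missing marks relate to pain or arm. The documents give no figures to size that bias.

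On objective i, the 24-hour mark carries 43.75% of the trapezoid weight. If an area were cut at 3 hours, which the plan does not say, it would be 0.125 of the full value under constant pain and about 0.06 to 0.34 under the assumed non-flat courses. This is a secondary outcome. The wording of its regression is ambiguous and should be settled, but it is not proof that a single score is intended.

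Overall this is a cheap improvement worth making before the sealed forms are opened.

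**What to change.** In 7.1 and 7.6:

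1. **Primary.** Estimate the 1-hour arm difference and its 95% CI, judged against the 20 mm margin, from a linear mixed model for repeated measures on the 5-minute, 1-, 2-, 3- and 24-hour scores. Include arm, time, arm-by-time and pre-injection VAS. The margin keeps its meaning: randomisation gives both arms the same expected baseline, so the difference in 1-hour means has the same target as the difference in changes.
2. **Forms without a pre-injection mark.** A standard fit with baseline as a covariate would drop these. To keep them, model the pre-injection score as a response with a common mean across arms.
3. **Objective i.** Take the time-weighted 5-minute to 24-hour contrast from the same model. Trapezoid weights in hours are 11/24, 23/24, 1, 11 and 10.5 at 5 minutes, 1, 2, 3 and 24 hours (total 24 − 1/12 = 23.92). State that this, and not the single 24-hour score, is tested, and whether condition stays in the model. Do not use an AUC truncated at the last available mark.
4. **Sensitivity.** Keep the planned t-test on complete forms, with its non-parametric alternative.

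The cost is SAP wording and a standard model in Stata, which 7.3 already names. The model relies on data missing at random and is less simple than a t-test. It does not help with unreturned forms, which 7.6 still excludes.
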